11.3 Safety Analysis

11.3.1 Analysis of Adverse Events (treatment-emergent, serious, and deaths)

Adverse events will be coded to a Medical Diction.ary for Regulatory Activities Terminology (MedDRA) version 18.1. Verbatim description and the MedDRA System Organ Class (SOC) and Preferred Term for all adverse events will be contained in the subject data listings.

For adverse events with partial start date (i.e., with only month and year are recorded), the following imputation rule will be applied: 15th of the month or fist dose date which one comes later. The imputed date will be used to derive TEAE analysis flag. The actual collected date will be displayed in all AE data listings.

All reported adverse events (regardless of treatment-emergent or not) will be included in a by- subject adverse event listing. Only OLE treatment-emergent adverse events will be included in summary tables. For this study, the AE reporting period is defined as 30 days following the last administration of study treatment; therefore, adverse events that occur up to 30 days following the subject's last dose in OLE are included as treatment-emergent events.

The incidence of treatment-emergent adverse events will be presented by the counts and percentages of subjects with adverse events. A subject will be counted only once in the incidence count for a MedDRA Preferred Term, although a subject may have multiple occurrences (start and stop) of an event associated with a specific MedDRA Preferred Term.

Severe adverse events and adverse events related to treatment (definitely, probably, possibly, or remotely) will be summarized OLE treatment group.

An adverse event is regarded as related to study medication if the relationship to study medication is definitely, probably, possibly or remotely related. Adverse events with missing relationship will be assumed to be treatment related. Adverse events with missing severity will be assumed to be severe in order to perform the most conservative statistical analysis.

Planned summary tables are listed below:

- Summary of treatment-emergent adverse events;
- Incidence of treatment-emergent adverse events by MedDRA System Organ Class and Preferred Term
- Incidence of treatment-emergent adverse events by MedDRA System Organ Class, Preferred Term, and maximum severity
- Incidence of treatment-emergent serious adverse events by MedDRA System Organ Class and Preferred Term

SK LS Protocol YKP3089C017

SAP-OLE Version Final_15May2021 Page 29 of 43

- Incidence of treatment-emergent adverse events leading to study drug discontinuation by MedDRA System Organ Class and Preferred Term
- Incidence of treatment-emergent adverse events leading to death by MedDRA System Organ Class and Preferred Term
- Incidence of treatment-emergent adverse events (all causality) by decreasing frequency in overall group reporting only preferred terms (no system organ class)

Deaths, serious adverse events, and adverse events leading to treatment discontinuation, will be listed including the OLE treatment group, start and stop dates of the adverse event, and onset day relative to the start of the OLE study drug. Details of listings that will be provided for the OLE-SE analysis population are as follows:

- Listing of subjects who died;
- Listing of subjects with treatment-emergent serious adverse events;
- Listing of subjects with treatment-emergent adverse events leading to study drug discontinuation.

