10 SAFETY ENDPOINTS

10.1 Adverse Events

For open-label extension analyses, treatment-emergent AEs are defined as AEs with onset after the start of OLE study medication, up to last dose date of OLE study medication + 30 days, or onset before start of OLE study medication and worsened after starting OLE study medication, up to last dose date of OLE study medication + 30 days.

AE relationship to study drug can be classified by the investigator as definite, probable, possible, remote or unrelated. AEs severity can be rated as mild, moderate or severe.

SAEs will be captured from the time of study drug administration in OLE to 30 days after the last dose of study drug, and will be monitored until resolution or stabilization.

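### SAP 11.3.1 sets month-only AE onsets to the later of the 15th and an unnamed first dose, with no same-month or end-date check, so AEs from earlier double-blind months can be flagged as emergent in the open-label extension (OLE)

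*SAP*

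**What the plan says.** SAP 11.3.1 has one rule for every AE whose onset has only month and year. The imputed onset is "15th of the month or fist dose date which one comes later. The imputed date will be used to derive TEAE analysis flag". The SAP has two first doses, one in the double-blind period and one in the OLE, and the rule names neither. It has no condition that the AE be recorded in the month of that dose, and no check against the AE end date.

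SAP 10.1 defines the flag. For the OLE, "treatment-emergent AEs are defined as AEs with onset after the start of OLE study medication", or "onset before start of OLE study medication and worsened after starting OLE study medication", in both cases up to 30 days after the last OLE dose. SAP 11.3.1 adds "Only OLE treatment-emergent adverse events will be included in summary tables". For the by-subject listing, "All reported adverse events (regardless of treatment-emergent or not) will be included", and AE listings show the collected date. Double-blind AEs are therefore in the data to which the flag is applied. The worsening condition in SAP 10.1 also presupposes them.

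**The concern.** A recorded month that lies wholly before the OLE start already settles that onset was pre-OLE. A rule that takes the later of two dates can override that. It can move an April event to a July OLE start and make it emergent by imputation alone, although SAP 10.1 would admit it only if it worsened. For subjects who came from placebo, an event that arose on placebo would then be tabulated as emergent on open-label drug.

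The flag decides what enters the OLE incidence tables by system organ class, preferred term and maximum severity. If the rule can be read in more than one way, two programmers can produce different tables from the same data.

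**Working it through.** The SAP gives no figure to reproduce; this is a check of date logic.

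**Example (dates chosen for illustration).** OLE start is 10 July 2014. Double-blind dosing starts on Day 2 and the OLE on Day 127 (Protocol Table 1 and 9.3.1), so the first double-blind dose is 125 days earlier, 7 March 2014. An AE is recorded as April 2014.
- First OLE dose as anchor: later of 15 April and 10 July = 10 July. It is flagged if onset on the dose date counts, and not flagged if onset must be strictly after it.
- First double-blind dose as anchor: later of 15 April and 7 March = 15 April. Not flagged.

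**Start-month errors.** Assume a 365-day year, with OLE start day s and true onset day d evenly spread within the same month.
- All pairs: 7 × 31² + 4 × 30² + 28² = 11,111.
- True OLE onsets (d ≥ s): 7 × 496 + 4 × 465 + 406 = 5,738.
- Pre-OLE onsets (d < s): 11,111 − 5,738 = 5,373.
- The imputed day is max(15, s) with the OLE anchor and 15 with the double-blind anchor.

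| Reading | Earlier-month AEs flagged | True OLE onsets dropped, start month | Pre-OLE onsets flagged, start month |
|---|---|---|---|
| A. OLE dose, on or after | 100% | 0/5,738 | 5,373/5,373 = 100% |
| B. Double-blind dose, on or after | 0% | 1,523/5,738 = 26.5% | 1,260/5,373 = 23.5% |
| C. Either dose, strictly after | 0% | 1,720/5,738 = 30.0% | 1,092/5,373 = 20.3% |

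In C, if onset on the dose date itself is not counted as a true OLE onset, the dropped share is 1,523/5,373 = 28.3%.

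Divided by 365, these are onset-days per subject: A flags 14.7 wrongly; B drops 4.2 and flags 3.5; C drops 4.7 (or 4.2) and flags 3.0. Total start-month error under B is (1,523 + 1,260)/11,111 = 25.0%. Its net error is (1,260 − 1,523)/365 = −0.7 onset-days.

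**Does the later-of clause do anything?** Under B and C the OLE flag is the same as if the 15th were always used. Only A gives the clause any effect on this flag.

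**Reach of reading A.** Of 126 double-blind days (18 weeks), 5,373/365 = 14.7 on average fall in the OLE start month. The other 126 − 14.7 = 111.3 (88.3%) fall in earlier months, and every month-only AE from them is flagged. If month-only AEs arise at the same daily rate in both phases, the wrongly added onsets as a share of true OLE month-only onsets are:
- 1-year OLE: 111.3/365 = 30.5%
- 5-year OLE: 111.3/1,825 = 6.1%
- 10-year OLE: 111.3/3,650 = 3.0%

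If the double-blind rate is half to twice the OLE rate, the ranges are 15.2-61.0%, 3.0-12.2% and 1.5-6.1%. The base is month-only onsets, not all AEs and not subject incidence.

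**The case against.** The case against reading A is substantial. In SAP Appendix 2 (14.1 to 14.3) the unqualified first dose of study drug is the double-blind one, since the OLE starts there on Day 127. Where the SAP means the OLE dose it usually says so (8.5, 8.6, 9). SAP 10.1 says after, and taken literally an onset on the dose date is not after it. The argument that only A gives the clause an effect assumes the sentence was written for this SAP. Yet the document carries text it does not use, such as the quality-of-life and multiple-testing references in section 15. A rule inherited from the separate double-blind SAP is plausible.

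This stands as a reason for moderate confidence, but it does not settle the matter. SAP 7.3 counts emergent AEs from the first dose, and the listings in 11.3.1 use "onset day relative to the start of the OLE study drug". The text supports more than one reading.

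A reader might infer that every OLE group is over-counted, or that the tables are inflated by 30%. The documents do not support that. They give no count of month-only AEs, and Protocol 10.3 asks for date and time of onset. Double-blind contacts are also closer together (visits every 2 to 4 weeks plus calls on Days 8, 22 and 36) than OLE visits (every 12 weeks from Visit 12), so partial dates may be rarer in the double-blind phase. In addition, "A subject will be counted only once in the incidence count for a MedDRA Preferred Term", so an added event matters only if the subject has no other OLE event of that term.

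A reader might also infer that the serious-AE table and the output titled "Listing of subjects with treatment-emergent serious adverse events" are inflated. That is uncertain, because SAP 10.1 captures SAEs from OLE dosing onward, which taken as written leaves double-blind SAEs out. Tables of AEs leading to discontinuation or death should change little, since only subjects who complete double-blind maintenance may enter the OLE.

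**Conclusion.** The rule is deficient as written and should be corrected before the OLE tables are run. On the reading that gives the clause an effect, it flags all month-only AEs from earlier double-blind months (about 88% of double-blind days), contrary to what the recorded month shows and without the worsening test in SAP 10.1. On the other readings earlier months are handled correctly. The start month then has errors in both directions: about 27-30% of true OLE onsets lost and about 20-24% of pre-OLE onsets flagged. Some start-month error is unavoidable when the day is missing.

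The percentages rest on even spread of OLE starts and onsets. The effect on the tables is unknown and may be small. The OLE analysis is descriptive, so no test or error rate is affected. Confidence is moderate because the anchor and the same-day rule are both open.

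**What to change.** - In SAP 11.3.1, name the first OLE dose.
- In SAP 10.1, make onset on or after the first OLE dose date treatment-emergent. SAP 8.6 already uses this form for medications.
- Use the later of the 15th and the first OLE dose only when the recorded month and year are those of that dose and the AE end date is not known to precede it.
- If a known end date precedes that dose, treat onset as pre-OLE.
- Otherwise use the 15th, but not later than a complete end date.

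The cost is a short edit in two sections and a few branches in the date-imputation program.

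The downside is directional. All start-month AEs of unknown order become OLE-emergent. Under even spread 5,373/11,111 = 48.4% of them predate the OLE, an over-count of 14.7 onset-days per subject before the end-date check. The double-blind anchor with on-or-after has 25.0% total error in that month and a net error of about −0.7 onset-days. Against reading A, wrongly flagged double-blind onset-days fall from 126.0 to 14.7. The over-count matches the conservative handling that 11.3.1 already gives to missing severity and relationship, and it should be stated in the SAP.

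The fix leaves one error untouched. In the month containing last OLE dose + 30 days, the 15th can fall on the wrong side of the cut-off. Under even spread 1,260/5,738 = 22.0% of true emergent AEs in that month are missed and 1,523/5,373 = 28.3% of later ones are flagged.

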1 PROTOCOL SYNOPSIS

Name of company	SK Life Science Inc
Title of study	A Multicenter, Double-Blind, Randomized, Placebo-Controlled, Dose-Response Trial of YKP3089 as Adjunctive Therapy in Subjects with Partial-Onset Seizures, with Optional Open-Label Extension
Protocol number	YKP3089C017
Phase of development	Phase 2b
Study duration	Baseline phase: 8 weeks Double-blind up-titration: 6 weeks Double-blind maintenance phase: 12 weeks Double-blind crossover to open-label extension: 2 weeks Blinded study drug taper: 3 weeks Open-label extension phase: Until development is stopped by SK Life Science Inc, or the product is approved for marketing, or any time at the discretion of SK Life Science Inc.
Indication	Partial-onset epilepsy
Study center(s)	Approximately 100 sites (multiple countries)
Number of subjects	400 randomized
Objectives	The primary objective of this study is to determine the effective dose range of YKP3089 as adjunctive therapy for the treatment of partial seizures. The trial will also evaluate the safety and tolerability of YKP3089 in the partial epilepsy population.
Inclusion and exclusion criteria	Subjects who meet all inclusion and no exclusion criteria listed in Section 7.3 and Section 7.4 of the protocol are eligible to enroll. Men and women 18 to 70 years of age, inclusive, will be permitted to enroll in this study. During the baseline, subjects must have at least 8 partial seizures, including only simple partial seizures with motor component, complex partial seizures, or secondarily generalized seizures without a seizure-free interval of greater than 25 days any time during the 8-week baseline despite appropriate doses of at least 1 and no more than 3 concomitant

	
AEDs. Subjects must have at least 3 of these partial seizures during each of the two consecutive 4-week periods in the baseline.
 
Patients who meet the above seizure criteria and continue to meet other inclusion/exclusion criteria will be randomly assigned to the treatment.

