The initial target dose for the open-label extension will be 300 mg/day. However, if a subject is not tolerating the 300 mg/day dose, YKP3089 dose may be reduced to a minimum of 50 mg/day. If the investigator feels that a subject requires a dose that is higher than 300 mg/day, the dose can be increased to a maximum of 400 mg/day once the target dose of 300 mg/day was reached. The dose adjustments may occur in weekly increments of 100-mg/day or 50-mg/day. However, the rate of change may be more rapid or slow as clinically indicated. No dose reductions are permitted if the subject is taking 50 mg/day YKP3089. If 50 mg/day YKP3089 is not tolerated, the subject will withdraw from the study. Monotherapy with YKP3089 will not be allowed. The investigator may add, remove, or adjust the dosage of concomitant AEDs, as clinically indicated. In the event of poor tolerability, the investigator may instruct the subject to take the dose of study medication in the evening or divide the total daily dose into 2 doses. Subjects will follow the schedule of study visits and assessments detailed in [Table 2](#). After 12 months of participation in the open-label extension phase, subjects will be re-evaluated. Those who are benefiting from treatment with YKP3089 may continue use of the drug at the discretion of the investigator, until development is stopped by SK Life Science Inc or the product is approved for marketing, or anytime at the discretion of SK Life Science Inc.

6.1.4.3 *Study Drug Taper: Subjects Leaving the Open-Label Extension*

Subjects who are withdrawn from the open-label extension study will taper YKP3089 according to the schedule described in [Table 6](#), unless for safety reasons the investigator judges it necessary to discontinue study drug immediately. The investigator is encouraged to discuss the tolerability criteria with the Sponsor or its designee.

Table 6. Study Drug Taper Schedule for Subjects Completing Open-Label Extension

Final open-label dose of YKP3089 (mg/day)	YKP3089 Dose During Taper (mg/day)		
	Week 1	Week 2	Week 3
50 or 100	None		
150 or 200	100	None	None
250 or 300	200	100	None
350 or 400	300	200	100

The final visit will take place 14 days after the subject's last dose, following taper and discontinuation of YKP3089; at any time during the open-label treatment; or after 12 months of open-label treatment if there is no additional treatment beyond that point.

6.1.5 *Dose Adjustments of Study Drug and Concomitant AEDs*

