8.2 Subject Disposition

Subject disposition during OLE will be summarized using the number of subjects who opted for open-label extension as the denominator. Summary results will include, the number and percentage of subjects who completed the open-label extension, and the number and percentage of subjects who discontinued during the open-label extension along with the distribution of the reasons for discontinuation. Results will be summarized by OLE treatment groups.

For summary tables the reasons for termination/withdrawal recorded on the eCRF will be mapped as follows:

Reason for Termination/ Withdrawal on eCRF	Reason for Termination/ Withdrawal in Summary Table
Withdrew consent for reason other than adverse event	Withdrawal by Subject
Withdrew consent due to adverse event	Adverse Event
Terminated by PI for adverse event	Adverse Event
Terminated by Sponsor's medical monitor for adverse event	Adverse Event
Protocol violation	Protocol Violation
Lack of efficacy	Lack of efficacy
Pregnancy	Pregnancy
Lost to follow up	Lost to follow up
Death	Death
Other	Other

By-subject data listings will include reason for termination/withdrawal as recorded on eCRF.

SK LS Protocol YKP3089C017

SAP-OLE Version Final_15May2021 Page 19 of 43

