8.5 Drug Exposure and Compliance

The extent of exposure to study drug as recorded on eCRF will be provided in a listing by-subject and by study week.

The following parameters will be derived:

- Exposure (days) = date of the last dose in OLE date of the first dose in OLE + 1
- Exposure (weeks) = (date of the last dose in OLE date of the first dose in OLE + 1)/7
- Exposure (months) = (date of the last dose in OLE date of the first dose in OLE + 1)/30.4
- Total subject years of exposure = sum of all subject total exposure days / 365.25.
- Modal daily dose defined as the dose taken the most days during OLE; in case of ties (i.e., 2 different dose levels taken the same number of days), modal dose will be defined as the highest dose between the two

Length of exposure (weeks and months) and modal dose will be summarized by OLE treatment groups using descriptive statistics.

The number and percentage of subjects for the following:

- exposure intervals: 0 to < 1 week,1 to < 2, 2 to < 4, 4 to < 12, 12 to < 24, 24 to < 48, 48 to < 96, 96 to < 144, 144 to < 192, 192 to < 240, 240 to < 288, 288 to <336, 336 to < 384, 384 to < 432, 432 to < 480, 480 to < 528, 528 to < 576, , >=576 weeks.
- exposure categories: >= 1 dose, >= 6, >= 12, >= 18, >= 24, >= 36, >= 48, >= 60, >= 72, >= 84, >= 96, >= 108, and >= 120 months.

Total subject years of exposure will be computed as sum of all subject total exposure days / 365.25 and reported in the summary table.

Drug accountability (tablets dispensed and tablets returned) will be listed by visit.

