9 EFFICACY ENDPOINTS

During OLE subjects will records number of seizures by seizure type in the daily dairy. Data from OLE seizure diary will be used to assess percent reduction in seizure frequency over time in subjects with longer exposure to YKP3089.

Percent reduction in seizure frequency will be calculated over the entire OLE phase (overall) and by both 6-month intervals after the start of OLE and cumulative intervals with 6-month increment.

Definitions and Derivations:

- The baseline seizure frequency per 28-day will be based on the baseline seizure diary collected prior to the first dose date in the DB period. This will be calculated by counting the number of seizures over the baseline period, dividing by the number of days in the baseline period with nonmissing seizure data, and then multiplying by 28.
- Overall seizure frequency per 28-day during OLE phase will be calculated by counting the number of seizures over the entire OLE phase, dividing by the number of days in the OLE phase with non-missing seizure data, and then multiplying by 28.
- Seizure frequency per 28-day by 6-month intervals during OLE phase will be calculated by counting the number of seizures reported during the respective 6-month interval, dividing by the number of days in the respective 6-month intervals with non-missing seizure data, and then multiplying by 28.

The following 6-months intervals will be defined for OLE seizure frequency per 28-day derivations:

6-Months Interval	OLE Phase Diary Study Days
1 – 6 Months	1 to 182
7 – 12 Months	183 to 365
13 – 18 Months	366 to 547
19 – 24 Months	548 to 730
25 – 30 Months	731 to 912
31 – 36 Months	913 to 1095

37 – 42 Months	1096 to 1277
43 – 48 Months	1278 to 1460
49 – 54 Months	1461 to 1642
55 – 60 Months	1643 to 1825
61 – 66 Months	1826 to 2007
67 – 72 Months	2008 to 2190
73 – 78 Months	2191 to 2372
79 – 84 months	2373 to 2555
85 – 90 months	2556 to 2737
91 – 96 months	2738 to 2920
97 – 102 months	2921 to 3102
103 – 108 months	3103 to 3285
109 – 114 months	3286 to 3467
115 – 120 months	3468 to 3650
>120 Months	>3650 (to last study day diary in OLE)

Study day 1 = day of the first dose in OLE phase.

 Seizure frequency per 28-day by cumulative intervals with 6-month increment during OLE phase will be calculated by counting the number of seizures reported during the respective cumulative intervals, dividing by the number of days in the respective cumulative intervals with nonmissing seizure data, and then multiplying by 28.

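### The open-label SAP reports adverse events and completion only as crude percentages although follow-up is open-ended; time-at-risk rates, interval incidence and Kaplan-Meier retention should be added

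*SAP*

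**What the plan says.** **Adverse events.** SAP 11.3.1: "The incidence of treatment-emergent adverse events will be presented by the counts and percentages of subjects with adverse events". A subject counts once per preferred term, and every table listed there has this form. No person-time rate, cumulative-incidence estimate or table by time interval is planned. Onset day is promised only in the listings of deaths, serious events and events leading to discontinuation.

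**Disposition.** SAP 8.2 reports "the number and percentage of subjects who completed the open-label extension", "using the number of subjects who opted for open-label extension as the denominator". Completion is not defined. The table of withdrawal reasons has no entry for sponsor closure or marketing approval other than the general category for other reasons.

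**Length of the extension.** The Protocol synopsis gives it as "Until development is stopped by SK Life Science Inc, or the product is approved for marketing, or any time at the discretion" of the sponsor; Protocol 6.1.4.2 and footnote b of SAP Table 1 agree. SAP 8.5 plans "exposure intervals: 0 to < 1 week,1 to < 2, 2 to < 4" weeks and so on up to at least 576 weeks. The last expected visit in SAP Appendix 2 is Visit 44, target day 2843.

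**Exposure.** SAP 8.5 also says: "Total subject years of exposure will be computed as sum of all subject total exposure days / 365.25". Length of exposure is summarized by group, with percentages of subjects reaching 6, 12, 18, 24, 36, 48, 60, 72 and more months. Subject-years are not used as a denominator for any event.

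**Groups and inference.** SAP 8.1 displays the four former randomized arms and their total. SAP 11.1 rules out inferential analysis.

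**The concern.** A crude percentage of subjects with an event rises with time on drug. When some subjects are observed for days and others for years, the figure describes the mix of follow-up as much as the drug. This affects the pooled column directly. It also prevents any reading of the extension against the 18-week double-blind period or against a study of another length.

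Percent completed has a similar weakness. In an extension that stops when the sponsor stops it, the percentage depends on when subjects entered and when the study closed, so it does not measure retention.

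The SAP avoids this problem for efficacy: section 9 uses seizure rates per 28 days in 6-month and cumulative intervals. Safety and tolerability is a stated objective (SAP 5), and long-term safety is the main thing the extension can add, but neither approach is carried over to adverse events.

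**Working it through.** The plan states no figure on this point, so there is none to reproduce. The check asks how far crude percentages move when the underlying risk is held constant.

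**Inputs from the documents**
- Extension length to the last expected visit: day 2843 − day 127 = 2716 days; 2716 / 365.25 = 7.44 years.
- Double-blind period: 126 days / 365.25 = 0.345 years.
- Longest exposure class: 576 × 7 / 365.25 = 11.0 years. This is a table category, not observed exposure, so 7.44 years is used below.

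**Inputs assumed** (not in the documents)
- Constant hazard r of a first event, 0.02 to 1.0 per year.
- Constant discontinuation hazard d, 0.10 to 0.80 per year.
- A common administrative end at T = 7.44 years.

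**1. Extension against the double-blind period.** Crude percentage at fixed follow-up t = 1 − exp(−rt).
- r = 0.10: 1 − exp(−0.744) = 52.5% against 1 − exp(−0.0345) = 3.4%, about 15 times.
- r = 0.02: 13.8% against 0.7%. r = 1.0: 99.9% against 29.2%.
- With discontinuation in the extension at 0.10 or 0.30 per year, the 52.5% falls to 38.7% or 23.7% (step 2), still about 11 or 7 times 3.4%.

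**2. Between former randomized arms.** Crude percentage = r/(r+d) × [1 − exp(−(r+d)T)]; mean exposure = [1 − exp(−dT)]/d. With r = 0.10 in both arms and d = 0.10 in the first (38.7%, mean exposure 5.25 years):

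| d in second arm | Mean exposure (years) | Crude % | Ratio |
|---|---|---|---|
| 0.15 | 4.48 | 33.8 | 1.15 |
| 0.20 | 3.87 | 29.8 | 1.30 |
| 0.30 | 2.98 | 23.7 | 1.63 |
| 0.50 | 1.95 | 16.5 | 2.35 |
| 0.80 | 1.25 | 11.1 | 3.49 |

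Over the first three rows the ratio runs from 1.17 to 1.73 at r = 0.02, and from 1.05 to 1.18 at r = 1.0.

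**3. Percent completed.** With d = 0.20 and completion read as still on drug at closure: exp(−0.20) = 81.9% if closed after 1 year, exp(−0.60) = 54.9% after 3, exp(−1.487) = 22.6% after 7.44.

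**4. What a rate recovers, and where it fails.** First events divided by time at risk gives 10.0 per 100 subject-years for d = 0.10, 0.30 and 0.80, where the crude figures are 38.7%, 23.7% and 11.1%. That result needs a constant hazard. Suppose instead a hazard of 1.0 per year for 3 months and zero afterwards. The crude percentage is 1 − exp(−0.25) = 22.1% whatever the later follow-up. Time at risk per subject is 0.221 + 0.75 × 0.779 = 0.805 years with 1 year of follow-up, and 0.221 + 3.75 × 0.779 = 3.142 years with 4. The rates are 27.5 and 7.0 per 100 subject-years, a 3.9-fold difference produced by follow-up alone.

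**The case against.** The strongest reply is that the displayed groups are well matched and nothing is tested. They come from 1:1:1:1 randomization, all subjects completed the double-blind phase, all convert to one target dose, and entry and closing dates are balanced in expectation. SAP 11.1 makes the analysis descriptive, and the SAP plans no comparison with double-blind rates. SAP 8.5 already shows exposure by group, total subject-years, and the percentage reaching 12, 24, 48 and 72 months.

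Much of this stands. A reader might infer that former arms with the same underlying risk will differ several-fold. The documents do not support that: they give no exposure by group, and step 2 needs about an 8-fold difference in discontinuation to reach 3.5 times. A reader might also infer that percent completed is biased between arms. It is not when yearly discontinuation is equal, because the arms share the same distribution of entry and closing dates. The absence of a withdrawal category for closure is a lesser point, since closure may be meant to count as completion; the missing definition is the fault.

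Three things do not fall away.
- Balance between arms does nothing for the pooled column.
- Equal retention is not guaranteed. Entry is a choice made after randomization, and the former placebo group first takes the drug at conversion.
- The exposure categories ignore censoring: a subject still on drug when the study closes at 40 months counts as not reaching 48 months, like one who withdrew at 40. Total exposure is also not time to first event, so a rate formed by hand is only rough.

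**Conclusion.** The point holds as a reporting gap. Crude percentages alone cannot describe long-term safety in an extension without a fixed end, and an undefined percent completed cannot describe retention.

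The effect is large for the pooled column and for any reading against the 18-week period: about 15-fold at an assumed hazard of 0.10 per year with full follow-up to 7.4 years, and 7- to 11-fold with the discontinuation rates assumed above. Between former arms it is probably modest, about 1.15 to 1.6 times for 1.5- to 3-fold differences in discontinuation at that hazard. Percent completed can read 82%, 55% or 23% for the same yearly discontinuation of 0.20, depending on the closing date.

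All hazards are assumed constant and none comes from the documents. No planned test is invalid. This is an inexpensive improvement that changes what the extension can say about long-term safety and retention.

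**What to change.** **SAP 11.3.1.** Keep the crude percentages and add:
- Subjects with a first event per 100 subject-years at risk, for all, serious and discontinuation events and for common preferred terms. Time at risk should run from the first extension dose to the first event or the end of the event window. That window closes 30 days after the last dose, whereas exposure in 8.5 stops at the last dose.
- Incidence by the 6-month intervals already set in SAP 9, with the number at risk in each. This covers early-onset events, for which a single rate can mislead (step 4).

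**SAP 8.2.** Define completion. Separate sponsor closure and transfer to marketed product from withdrawal. Add Kaplan-Meier time from first extension dose to discontinuation, censoring those administrative ends, with estimates at 1, 2, 4 and 6 years.

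Any confidence intervals should be labelled descriptive, in line with 11.1.

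**Cost.** Event dates, dosing dates and end-of-study status are already collected. Time to first event and an administrative censoring reason must be newly derived; the latter may need review of subjects recorded under other reasons. A few outputs are added. SAP 4 allows revision before the extension database lock.
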